10. OBJECTIVES AND ENDPOINTS

The overall purpose of the PARABLE trial is to assess the impact of LCZ696 on functional, structural and biochemical abnormalities as surrogates of cardiovascular disease in an asymptomatic cohort with cardiovascular risk factors and elevated NP (brain type natriuretic peptide (BNP) and N-terminal of the prohormone BNP (NT-proBNP)).

10.1 Objectives

Primary objective:

1. To assess the impact of LCZ696 (sacubitril/valsartan) versus angiotensin II receptor blocker (ARB) (valsartan) on left ventricular diastolic function over 18 months.

Secondary objectives:

1. To assess the impact of LCZ696 versus valsartan therapy on atrial and ventricular structure and function over 9 and 18 months.
2. To assess the impact of LCZ696 versus valsartan therapy on cardiovascular and non-cardiovascular adverse events, including prior to and post onset of Covid19 pandemic.

Exploratory objectives:

1. To assess response to LCZ696 based on genetic variants associated with the expression and metabolism of BNP (e.g. neprilysin, Nppb, Npra and Nprc genes).
2. To assess the impact of LCZ696 versus valsartan on biochemical markers of fibro-inflammation and myocardial damage at 9 and 18 months.
3. To assess the impact of LCZ696 versus valsartan on biochemical markers of renal function
4. To correlate the impact on left ventricular dysfunction and biochemical markers in order to understand the mechanism of benefit of LCZ696 versus ARB therapy in modulating fibro-inflammation, myocardial damage, and cardiac function.
5. To provide further information in the target subject population on the safety and tolerability of LCZ696 versus valsartan.
6. To assess the impact of LCZ696 versus valsartan on Health-Related Quality of Life and cognitive function (through the administration of questionnaires) in the target subject population.
7. To assess the difference between groups in terms of atrial and ventricular arrhythmia measured non-invasively over 5-7 days using Holter monitoring
8. To assess response of immune cells to sacubitril/valsartan
9. To evaluate if the treatment effects observed during the 18-month PARABLE study persist nine-months after study drug discontinuation

10.2 Endpoints

Primary endpoint:

Change in left atrial volume index (LAVI) measured by cMRI over 18 months.

Secondary endpoints:

1. Left ventricular function using Doppler Echocardiography (average E/e') between baseline and 18 months
2. Left atrial volume index (Doppler Echocardiography LAV)/BSA* between baseline and 9 months
3. Left atrial function measured as total cMRI LAEF ((LAVimax-LAVimin)/LAVimax) over 18 months
4. Left atrial function measured as cMRI left atrial stroke volume index (LAVmax-LAVmin)/BSA*, or LAVimax-LAVimin over 18 months
5. Left ventricular structure (cMRI LVMi indexed to BSA*) over 18 months
6. Left ventricular function (cMRI LVEF) over 18 months
7. Measures of vascular compliance (ABPM pulse pressure) between baseline and 18 months
8. Change in log transformed NT-proBNP between baseline and 18 months
9. Time to first all cardiovascular death and major adverse cardiac events (MACE) requiring hospitalisation over 18 months. MACE includes arrhythmia (including atrial fibrillation/flutter), transient ischaemic attack, stroke, valvular heart disease, myocardial infarction, peripheral or pulmonary thrombosis/embolus or heart failure
10. Primary endpoint analysed per protocol.

*BSA calculated using the DuBois formula

Exploratory endpoints:

11. Left atrial function measured as cMRI left atrial cardiac index ((LAVimax-LAVimin) x heart rate) between baseline and 18 months

12. Left atrial function as cMRI myocardial strain measured using feature tracking
13. Left ventricular structure (as cMRI LVESV, LVEDV, Fractal Analysis), all indexed to BSA* between baseline and 18 months
14. Left ventricular function, measured as cMRI left ventricular stroke volume index (LVESVi-LVEDVi) between baseline and 18 months
15. Left ventricular function, measured as cMRI left ventricular cardiac index ((LVESVi-LVEDVi) x heart rate) between baseline and 18 months
16. Left ventricular function as cMRI myocardial strain using feature tracking between baseline and 18 months
17. Left ventricular function as cMRI e'
18. Evaluation of treatment effects on cMRI measures of right atrial and structure and function (RAVI, RAEF, RVEF, SV, CI, E', E/e')
19. Left atrial function using Doppler Echocardiography (E/A ratio)
20. Left ventricular structure using Doppler Echocardiography (LVMI, LVESVI, LVEDVI)
21. Left ventricular function using Doppler Echocardiography (LVEF, stroke volume (SV), cardiac index (CI), Lateral or medial e' and lateral or medial E/e')
22. Change in log transformed BNP, NTproBNP/BNP ratio and other related peptides, e.g. ANP, urinary cGMP between baseline and 9 months and baseline and 18 months
23. Change in the following parameters of 24-hour ABPM between baseline and 9 months and baseline and 18 months: Systolic blood pressure, diastolic blood pressure and heart rate
24. Change in resting (clinic measured) systolic blood pressure, diastolic blood pressure and heart rate between baseline and 9 months and baseline and 18 months
25. Incidence of all cardiovascular death and MACE requiring hospitalisation over 18 months
26. Incidence of all cardiovascular related serious adverse events (SAEs) over 18 months
27. Incidence of all-cause death and SAEs requiring hospitalisation over 18 months

28. Incidence of all SAEs over 18 months
29. Incidence of all-cause adverse events (AEs) by system organ class over 18 months
30. Time to first event analysis using Kaplan Meier survival curves for cardiovascular death or MACE requiring hospitalisation, cardiovascular-related SAEs, death or all-cause emergency hospitalisations, all-cause SAE
31. Impact of LCZ696 on endpoints in a subset of patients with or without baseline atrial cardiomyopathy, using EHRA/HRS/APHRS/SOLAECE 2016 consensus definition; a complex of electrophysiological (e.g. atrial fibrillation, atrial flutter), structural/architectural (e.g. LAVI >34ml/m²) or contractile (e.g. LAEF, elevated E/A ratio) on cMRI or Doppler Echocardiography, at 9 and 18 months
32. Impact of LCZ696 on prevalent and new onset atrial cardiomyopathy using EHRA/HRS/APHRS/SOLAECE 2016 consensus definition (defined as a complex of electrophysiological (e.g. atrial fibrillation, atrial flutter), structural/architectural (e.g. LAVI >34ml/m²) or contractile (e.g. LAEF, elevated E/A ratio) on cMRI or Doppler Echocardiography) at 9 and 18 months
33. Impact of LCZ696 on primary and secondary endpoints, at 9 and 18 months dependent on BNP above or below 50pg/mL, median BNP, NTproBNP and NTproBNP/BNP ratio at baseline
34. Correlation between Doppler Echocardiography and cMRI measures of the following at baseline and 18 months:
 - Left atrial structure and function (LAVi, LAEF)
 - Left ventricular structure and function (e.g. LVMi, LVSVi, LVCi, LVEF, e')
 - Correlation of cMRI-e' with left atrial and left ventricular feature tracking analysis
35. Change in the numbers of patients with progression of left ventricular dysfunction, defined using Doppler Echocardiography as: ejection fraction <50% with change of >5%; and/or lateral E/e' >13 or average E/e' >14 (with change >2); and/or lateral e' <9, with reduction >2 over 9 and 18 months
36. Pharmacogenetic response to therapy (i.e. change in primary and secondary endpoints) dependent on status of common genetic variants (or proxies in high linkage disequilibrium) associated with the expression and metabolism of natriuretic peptide, sacubitril and valsartan (e.g. CES, CYP2C9, NPRA, NPRB, NPPB, NPPA, NPRC (NPR3), MME, FURIN, CLCN, DPP4) at 9 and 18 months

37. Change in blood biomarkers of collagen turnover (e.g. Col1A1, PICP, PIIINP), ECM turnover (e.g. MMP-2, MMP-3, MMP-9, TIMP-1, TIMP-4), myocardial damage (hsTroponin), fibrosis (e.g. Galectin-3, sST-2), inflammation (e.g. IL-1R1, IL-R2, IL-2RA, IL-6RA, IL-6, TNF- α R1/R2, MCP1, CT1, GDF15 and RAAS (e.g. PRA, aldosterone), GP6, creatinine, ANP, uPAR, CD163, uPA, PON3, TR-AP, E/P-selectins, vWF, cystatin B, TF-PI between baseline and 18 months
38. Change in eGFR, creatinine, albumin creatinine ratio and urinary biomarkers of natriuretic peptide (e.g. cGMP, ANP) between baseline and 9 months and baseline and 18 months
39. Correlation between Doppler Echocardiography and cMRI measures of the following:
 - Left atrial structure and function (LAVI, LAEF, LVEF, SV, CI, E', E/e')
 - Left atrial and structure and function (LAVI, LAEF, LVEF, SV, CI, E', E/e') and pericardial and epicardial fat.
 - Right atrial and structure and function (RAVI, RAEF, RVEF, SV, CI, E', E/e') and pericardial and epicardial fat.
40. Change in cognitive function as measured by the Standardised Mini-Mental State Examination (MMSE) between baseline and 9 months and baseline and 18 months
41. Change in cognitive function as measured by the Montreal Cognitive Assessment tool (MoCA) between baseline and 9 months and baseline and 18 months
42. Change in quality of life as measured using the EuroQoL-5D-5L instrument (overall summary score and individual domain score) between baseline and 9 months and baseline and 18 months
43. Difference between groups in terms of CD14+, CD16+/- monocyte RNA expression profile, in a sub-set of subjects, between baseline and 9 months and baseline and 18 months
44. Impact of LCZ696 on biomarkers of angiogenesis, hypoxia, cardiac remodelling, cell adhesion, platelet activation, coagulation, chemotaxis, catabolic stress, inflammation and fibrosis which will be assessed using Olink CVIII proseek panel, between baseline and 18 months
45. Difference between treatment groups in incidence of atrial fibrillation/flutter, paroxysmal supraventricular tachycardia and other atrial or ventricular arrhythmias measured non-invasively in a sub-set of subjects over 5-7 days using continuous ECG monitoring

46. Pharmacogenetic responses to therapy dependent on polygenic risk score of blood pressure, atrial fibrillation, atrial dilatation associated gene variants and established pharmacogenetic gene variants of natriuretic peptide pathway and sacubitril (e.g. NPPB, NPPA, NPRC (NPR3), MME, FURIN, CLCN, DPP4, KLKB1, CES1 gene variants) at 18 months
47. Subgroup analyses on primary outcome and secondary endpoints (pre-specified subgroups include above and below median age and BMI, eGFR (above and below 90mls/min); gender, obesity, vascular disease, hypertension, diabetes, atrial fibrillation/flutter, valve disease)
48. Use of circulating metabolomics profile to identify responders to LCZ696 (based on primary and secondary endpoints)
49. Evaluation of secondary and exploratory endpoints in a sub-set of subjects, 9 months after completing therapy with IMP (extension analysis/9 months follow-up sub-study)
50. Evaluation of primary and secondary endpoints in total follow up period and prior to Covid19 restrictions implemented (13 March 2020)
51. Additional novel and established biomarkers outlined above measured in serum, plasma, or urine profiling using proteomic, transcriptomic, epigenomic, and metabolomic approaches
52. Evaluation of health economic analysis using cost-benefit analysis and cost-benefit analysis.

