Appendix 5. Immediate reporting to sponsor removed. Medical sign-off of SAE form added.

Version 6.0	Approval date: 04 Sept 2017. Effective date: 31 Oct 2017
--------------------	---

Substantial amendments

Section 10.1. Safety has been removed as an exploratory objective and added as a secondary objective.

Section 10.2. Safety has been removed as an exploratory endpoint and added as a secondary endpoint.

Section 10.2. The first endpoint (relating to cMRI LAVI and 9 months) has been removed.

Section 10.2. The second endpoint (relating to cMRI parameters of left ventricular structure and function) has been adjusted to remove assessment at 9 months.

Section 10.2. Secondary endpoint to also include change in BNP.

Section 12.4.17. MRI will only be performed at baseline and 18 months (9 month MRI removed).

Section 12.4.17. St Vincent's University Hospital has been added as a site for cMRI.

Section 12.4.17. 'Use of gadolinium containing contrast' has been removed and reference to gadolinium has been deleted.

Non-substantial amendments

Section 12.1. The following text was deleted as it does not relate to the screening visit 'If the patients is taking an ACE inhibitor, they will be instructed to stop taking this medication 36 hours before visit 2)'.
'

Table 2. The 'Where to record source data' column was updated (to reflect that the CRF can be used as the source document for some data).

Table 2. Footnote added 'Baseline echo must be performed within 90 days prior to baseline'.

Section 12.4.4. The speed, duration and temperature settings on the centrifuge were updated.

Section 12.4.16. Text added 'A baseline echo must be performed within 90 days prior to baseline visit'.

Section 13.10. The WebEz Helpdesk must be contacted with a request for emergency unblinding (previously the clinical trial project manager could be contacted).

Section 14.1. The following text was added 'Abnormal signs and symptoms identified during the physical and cardiac exam may also constitute an adverse event if they were not present at baseline'.

Section 14.1. The note to refer to the EMA IME list for adverse event assessment of seriousness was deleted.

Section 14.8. The email address of the Novartis pharmacovigilance department was updated.

Section 15. All deviations will now be recorded in a Deviation Log according to SOP (GBT-GCP-FM-28).

Section 25.1. The study timelines were updated.

Version 7.0	Approval date: 27 November 2018. Effective date: 01 March 2019

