--------------------	---

Substantial amendments

Section 10.1. Secondary objectives. The following objective was added:

To assess response to LVZ696 based on genetic variants of the NPPB, NPRA and NPRC genes (e.g. rs5068, rs198389).

Section 10.1. Exploratory objectives. The following objectives were added:

To assess the difference between groups in terms of atrial fibrillation measured non-invasively over 5-7 days using Holter monitoring

To assess response of immune cells to sacubitril/valsartan

Section 10.2. Secondary endpoints.

The following was added to bullet point 4. e.g. ejection fraction, Lateral/medial e' and lateral/medial/average E/e'.

The following were added as secondary endpoints:

Response to sacubitril/valsartan based on genetic variants of the NPPB, NPRA and NPRC genes (e.g. rs5068, rs198389);

Change in the numbers of patients with progression of left ventricular dysfunction, defined as: ejection fraction <50% with change of >5%; and/or lateral E/e' >13 or average E/e' >14 (with change >2); and/or lateral e'<9, with reduction >2.

Section 10.2. Exploratory endpoints: The following were added:

Difference between groups in terms of immune system response, e.g. CD14+, CD16+/- monocyte RNA expression profile;

Difference between groups in terms of atrial fibrillation measured non-invasively over 2-7 days using Holter monitoring.

Section 11.2.2. Exclusion criteria No. 14 amended so that raised LFTs are limited to AST and ALT.

Section 16.1. Description of statistical methods. The tests to be used to analyse continuous variables are described depending on their ability to be transformed or not. A plan for missing data is included. A description of how demographic and clinical characteristics will be presented is outlined. Further detail is

given on how to analyse primary and secondary outcomes and the variables to be considered when adjusting.

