12.3 Follow up visits (Visits 3-11)

Table 2 outlines the schedule of clinical assessments, blood sampling, imaging and follow-up that will apply in PARABLE. Follow-up visits will take place in the STOP-HF Service, St Michael's Hospital, Dun Laoghaire.

A follow-up visit will also take place two weeks after each dose titration (i.e. at week two and four and six).

If any subject refuses to return for these assessments or is unable to do so, every effort should be made to contact him/her by telephone and these attempts should be recorded in the subject's paper case report form (pCRF). If one visit is postponed or brought forward, it should not result in the next visit being postponed or brought forward. The next visit, if at all possible, should adhere to the original time schedule.

Table 2. Study assessments and procedures

Visit number	1	2	3	4	5	6	7	8	9	10	11	12
Assessment	Wk-2 Screening	D0 Baseline	Wk 2	Wk 4	Wk 6	Wk 13 / Mth 3	Wk 26 / Mth 6	Wk 39 / / Mth 9	Wk 52 / Mth 12	Wk 65 / Mth 15	Wk 78 / Mth 18 (EOS)	Mth 27 (Optional sub-study)
			± 3d	± 3d	± 3d	± 7d	± 7d	± 7d	± 7d	± 7d	± 7d	± 28
Assessment of eligibility	X											X
Pregnancy test (WOCBP)	X	X	X	X	X	X	X	X	X	X	X	X
Informed consent	X											X
Randomisation		X										
Medical history	X											
Physical exam	X	X	X	X	X	X	X	X	X	X	X	X
Height (H) and weight (W)		H/W						W			W	H/W
Waist/hip circumference		X						X			X	X
Vital signs (BP and pulse)	X	X	X	X	X	X	X	X	X	X	X	X
Natriuretic peptide	X [#]	X	X	X	X	X	X	X	X	X	X	X
Biomarkers		X			X	X	X	X	X	X	X	X
U&E, LFT, Alk phos	X (no alk phos)	X	X	X	X	X	X	X	X	X	X	X
Haematology	X	X						X			X	X
eGFR	X	X						X			X	X
HbA1c, lipid profile, iron studies		X						X			X	X
cGMP (urinary)		X			X	X		X			X	X
ABPM		X						X			X	X
Electrocardiography (ECG)		X						X			X	X
Doppler echocardiography	X [*]	X [†]						X			X	X
Cardiac MRI [‡]		X									X	
Questionnaires ^{**}		X						X			X	X
Concomitant medications	X	X	X	X	X	X	X	X	X	X	X	
Adverse events			X	X	X	X	X	X	X	X	X	X
Dispense medication		X	X	X	X	X	X	X	X	X		
Drug accountability			X	X	X	X	X	X	X	X	X	
Holter monitor (optional)											X	

*Source: results of these assessments may be filed in the Subject Study File on the original source document (questionnaires) or a copy of the source document (e.g. laboratory report, Echo report, ECG (this must be a copy of the original), ABPM printout etc.)

‡ Echo may be needed at Visit 1 if one hasn't been performed in the previous six months.

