12.4.4 Biomarkers

Peripheral blood samples and plasma for biomarker analysis will be drawn at the timelines shown in Table 2. Samples will undergo immediate serum separation by centrifuge at 1500 rcf (relative centrifugal force) for 15 minutes at 21°C. The serum and plasma will then be separated into aliquots and stored at -80°C. They will be

transported on dry ice to the Conway Institute, University College Dublin for simultaneous analysis of selected biomarkers from the Table below using validated analytical techniques:

- | | |
|--------------|-------------------|
| • Col1A1 | • Aldosterone |
| • PICP | • Creatinine |
| • PIIINP | • IL-6 |
| • MMP-2 | • IL-1R1 |
| • MMP-3 | • IL-R2 |
| • MMP-9 | • IL-2RA |
| • TIMP-1 | • IL-6RA |
| • TIMP-4 | • IL-17RA |
| • GP6 | • TNF-alpha R1/R2 |
| • sST-2 | • ANP |
| • hsTroponin | • MCP1 |
| • Galectin-3 | • CT1 |
| • PRA | • GDF15 |
| • uPAR | • TR-AP |
| • CD163 | • E/P-Selectins |
| • uPA | • vWF |
| • | • Cystatin B |
| • PON3 | • TF-P1 |

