25.1 Timelines and study duration

Start date: FPFV: 16 December 2015

End date:

- 18-month treatment period: LPFV: December 2018. FPLV: Oct 2017 and LPLV: December 2020
- 9- month follow-up (regression) substudy: FPFV: July 2019; LPLV: May 2021

Study Report date: CSR to be made available within 12 months after study completion.

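### Endpoint 45 is labelled incidence but rests on one optional month-18 Holter with no baseline recording, so it measures arrhythmia present at month 18; endpoint 43 needs a baseline cell sample that the protocol does not describe

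*Combined protocol and SAP*

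**What the plan says.** **Arrhythmia.** Endpoint 45 in Section 10.2 reads "Difference between treatment groups in incidence of atrial fibrillation/flutter, paroxysmal supraventricular tachycardia and other atrial or ventricular arrhythmias", assessed in a subset by 5 to 7 days of continuous ECG monitoring. In Table 2 (Section 12.3) the row beginning "Holter monitor (optional" is marked at Visit 11 only. Exclusion criterion 4 (Section 11.2.2) removes persistent AF and no other form. Endpoint 47 lists AF/flutter among the prespecified subgroups, so patients with such a history are expected in the trial. Section 16.1 assigns categorical endpoints to a generalised linear model, binomial for prevalence and Poisson adjusted for patient-years for incidence rates. The synopsis (exploratory objective 2) speaks of response to therapy, while Section 10.1 (exploratory objective 7) speaks of a difference between groups.

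**Monocyte RNA.** Endpoint 43 reads "Difference between groups in terms of CD14+, CD16+/- monocyte RNA expression profile, in a sub-set of subjects, between baseline and 9 months", and continues to baseline and 18 months. Exploratory objective 8 is "To assess response of immune cells to sacubitril/valsartan". On sample handling, Section 12.4.4 says "The serum and plasma will then be separated into aliquots and stored at -80°C". The document history records that the endpoint entered with Version 7.0: "Approval date: 27 November 2018. Effective date: 01 March 2019". Section 25.1 gives "18-month treatment period: LPFV: December 2018".

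**The concern.** Incidence means events that arise in people who were free of them at the start of a known period of observation. Endpoint 45 has neither element. Without a baseline recording, a patient with long-standing paroxysmal AF who shows it at month 18 counts the same as one who developed it on treatment. A report that keeps the word could present pre-existing arrhythmia as a drug effect on new arrhythmia. The label also steers the analysis to a rate model whose denominator the design does not supply.

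Endpoint 43 has a related weakness. It is defined as change from baseline, but the protocol does not show that a baseline measurement exists. If it does not, the analyst may be tempted to let an early on-treatment sample stand in for it. That would remove any early drug effect from the estimate.

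**Working it through.** **1. What one recording can show.** Set side by side: Holter at Visit 11 only (Table 2); persistent AF alone excluded (Section 11.2.2); AF/flutter a planned subgroup (endpoint 47). The observable outcome is arrhythmia present or absent during the month-18 recording. The rhythm information scheduled before treatment is the medical history at Visit 1 and the resting 12-lead ECG at Visit 2, which Section 12.4.13 requires to last at least 10 seconds. These can identify known AF/flutter but cannot exclude silent paroxysms.

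**2. Why patient-years do not fit.** Treatment lasts 78 weeks x 7 = 546 days. The recording covers 5/546 = 0.9% to 7/546 = 1.3% of it. Let x of n recorded patients be positive:
- Proportion: x/n.
- Rate with the treatment period as denominator: (365.25/546) x/n = 0.67 x/n per patient-year.
- Rate with recording time as denominator: (365.25/7) x/n = 52 x/n to (365.25/5) x/n = 73 x/n per patient-year.

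The two candidate rates differ by a factor of 546/7 = 78 to 546/5 = 109, and the plan does not choose between them. The proportion needs no such choice.

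**3. Endpoint 43: dates.** Visit 2 is up to two weeks after Visit 1 (Section 12.1).
- Last first visit 1 to 31 December 2018, plus 14 days: last baseline 15 December 2018 to 14 January 2019.
- Against the effective date, 1 March 2019: the last baseline is 46 to 76 days earlier.
- Against the approval date, 27 November 2018: the last baseline is 18 to 48 days later.
- Cross-check: Section 25.1 also gives the last visit of the treatment period as December 2020. Minus 546 days, that puts the last baseline at 4 June to 4 July 2019, after the effective date. Going forward from the stated last first visit, month 18 falls on 13 June to 13 July 2020, which is 141 to 201 days before December 2020; the visit window is 7 days. The two dates in Section 25.1 do not fit each other unless final visits ran late, and the protocol does not say that they did.

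**4. Endpoint 43: how many baselines could fall under Version 7.0.** Assumptions: 250 patients and uniform accrual. The first baseline lies between 30 December 2015 (stated first visit plus 14 days) and 3 May 2016 (first last visit at the end of October 2017, minus 546 days). The count is 250 x (days from cut-off to last baseline) / (days of accrual).

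| Last baseline | After effective date | After approval date |
|---|---|---|
| 14 January 2019 | 0 | 48/1111 to 48/986: 11 to 12 |
| 4 July 2019 | 125/1282 to 125/1157: 24 to 27 |219/1282 to 219/1157: 43 to 47 |

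So between 0 and 47 of 250 (0% to 19%) had a baseline visit at which Version 7.0 could have applied. These are counts of visits, not of samples.

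**5. Endpoint 43: samples.** Table 2 has no cell or RNA row at any visit. Section 12.4 describes no monocyte isolation, no RNA preservation and no rule for choosing the subset.

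**The case against.** **Arrhythmia.** Endpoint 45 never claims new-onset arrhythmia, and randomisation should balance pre-existing paroxysmal arrhythmia between arms. Much of this stands: a between-arm comparison at month 18 is legitimate, and a reader who infers that the missing baseline recording makes it invalid goes too far. If follow-up is nearly equal, the choice of denominator would also change the ratio between arms very little. Two things remain. The comparison estimates a difference in prevalence, whatever it is called. And the Holter is optional and comes 18 months after randomisation, so balance in the recorded subset is not guaranteed by randomisation alone.

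**Monocyte RNA.** A reader might infer that only serum and plasma were kept, that no patient has a baseline cell sample, and that the immune-cell objective therefore cannot be met. The documents do not support any of these.
- Section 12.4.4 covers the listed biomarkers. Section 22.5 requires consent to biobank blood without naming a fraction, and Appendix 9 names whole blood as a cryovial type for the month-27 visit.
- Table 2 is not a full inventory: endpoints 36 and 46 need genotyping, yet it has no DNA row. Sampling methods sit in a laboratory manual that is not among the documents.
- Approval preceded the last baseline visits, and Section 15.1 bars implementation only before approval. Section 22.4 requires both regulator and ethics approval, which makes the effective date the safer test but not a conclusive one.
- Objective 8 names no baseline. A between-arm comparison after baseline could address it.

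Equally, if silence in Table 2 is read as no cells at baseline, it must be read as none at months 9 and 18. It cannot be assumed that post-baseline cell data exist.

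**Conclusion.** The arrhythmia point holds. Endpoint 45 as scheduled measures arrhythmia present during one month-18 recording in an optional subset; it does not measure incidence, and a patient-years rate would be arbitrary by a factor of about 78 to 109. The effect on the result cannot be sized, because the protocol gives neither the size of the subset nor the prevalence of AF/flutter history.

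The monocyte point holds in a narrow form. The protocol describes no baseline cell or RNA sample for an endpoint defined from baseline, and by the effective date and the stated last first visit the endpoint came into force after the last baseline. Other readings of the dates allow up to about 47 of 250 baselines under Version 7.0, assuming uniform accrual. That the objective is unattainable is not shown: it can still be addressed if post-baseline cell samples exist.

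Both endpoints are exploratory. The primary and secondary analyses are not touched.

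**What to change.** **Endpoint 45.** Restate it as the proportion of patients with arrhythmia during the month-18 recording. Compare arms with the binomial model of Section 16.1, adjusted for AF/flutter history (Visit 1 medical history, Visit 2 ECG). Report by arm how many patients had a recording. Limit any statement about new arrhythmia to patients without such history, and call it newly detected, because a resting ECG does not exclude earlier paroxysms. Align the synopsis objective with the difference-between-groups wording of Section 10.1. The cost is a change of wording, with covariates already scheduled. The downside is a weaker claim from an optional subset.

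**Endpoint 43.** State when, from whom and how pre-treatment monocyte samples were taken. Limit both change-from-baseline comparisons to patients with a documented pre-treatment sample. If there are none, restate the endpoint as a between-arm comparison at whichever post-baseline visits were actually sampled, and rule out an on-treatment sample as baseline. Reconcile the last-first-visit and last-visit dates in Section 25.1. The cost is a check of the sample records and a change of wording. A comparison without baseline is likely to be less precise, and it is possible only if post-baseline samples exist.
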